23. DRUG SHIPMENT

Ibrutinib will be considered as an investigational agent for the purpose of this study. The Vanderbilt Investigational Pharmacy will be the central pharmacy for receiving ibrutinib from Janssen Scientific Affairs and then shipping it to individual site investigational pharmacy. Drug accountability logs will be maintained. All sites will perform IP destruction on site. Each site will send drug destruction and hazardous waste policy to the coordinating center (at [contact]) for review. Study drug destruction at the participating sites will be performed after the approval from the coordinating center. Documentation of the review and approval will be maintained in the study binder and at each participating site. Any drug that has been prepared but not dispensed, returned by the subject, expired, damaged, or otherwise deemed to be unusable will be destroyed on site according to the sites SOP for destruction. Each site will dispose of drug on site according to their SOP for destruction. Please refer to the IP Management Plan for additional details.

24. STATISTICAL ANALYSES PLAN

24.1 Analysis Plan

The statistical analysis plan will address the primary aim: To study the use of ibrutinib starting between day 60 and day 90 after allogeneic HCT until 12 months post HCT to improve the PFS at 12 months post HCT by 25% compared to historical controls. This will be restricted to cohort A which includes the diagnoses of CLL and MCL, only.

- PFS is defined as time to progression, or relapse of the underlying disease for which transplant was undertaken, or death from any non-relapse causes, starting from the date of stem cell transplant (SCT).
- We will estimate the 12-month PFS rate with a 95% confidence interval using the method of Kaplan-Meier and using the Greenwood variance estimator, and we will compare this estimate with the rate in the historical controls.
- Historical data
 - In a study by Sobecks et al⁵³, the outcomes of patients with CLL after ablative (n=163) and reduced intensity conditioning (RIC) 134 were reported. Outcomes were stratified based on when the HCT occurred (< 2000, or ≥ 2000). We expect the majority of patients with CLL on the proposed study to be undergoing RIC allo HCT, thus relevant data (≥ 2000 and RIC allo HCT) are taken into account for sample size analyses. One year PFS was 62% (95% CI 51-72).
 - In a study by Urbano-Ispizua et al⁵⁴, the outcomes of patients with MCL undergoing ablative (n=149) and RIC (n=351) allo-HCT was reported. The 1y PFS for patients with MCL (personal communication, CIBMTR) was 52% (95% CI 47-56)
- The proportion of patients with CLL and MCL enrolling in this study will not be known at the start of the study or be controlled for during the accrual period. Thus, we studied the impact on power of varying proportions of these two diagnoses on outcome for a given effect size.
- We will compare our overall PFS rate with the weighted average of the historical rates in CLL and MCL, using the proportion of our sample with each of these two diagnoses as the weights.

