10. ELIGIBILITY CRITERIA: EXCLUSION

Pre-SCT

1. Progression of CLL or MCL or FL or HD at time of transplant
2. Use of Coumadin (warfarin) or other vitamin-K antagonists for anticoagulation. Non-coumadin anticoagulation is permitted.
3. Known CNS involvement
4. Active uncontrolled bacterial or invasive fungal infections
5. History of malignancy other than the underlying disease unless treated with a curative intent and/or no evidence of disease for at least 3 y OR expected to be cured with SCT
6. Planned use of post-HCT cyclophosphamide for GVHD prophylaxis
7. Anticipated planned donor lymphocyte infusion in the first 3 months post-SCT
8. T deplete HCT
9. Umbilical cord HCT
10. History of stroke or intracranial hemorrhage within 6 months of enrollment.

11. Clinically significant cardiovascular disease such as uncontrolled or symptomatic arrhythmias, congestive heart failure, or myocardial infarction within 6 months of Screening, or any Class 3 (moderate) or Class 4 (severe) cardiac disease as defined by the New York Heart Association Functional Classification.
12. Known HIV
13. Active Hepatitis B or C virus
14. Child-Pugh Class C

Prior to Administration of Ibrutinib (Day 60-Day 90 Post SCT)

1. In the critical care unit, or use of mechanical ventilation or use of renal replacement therapy at any time post HCT and prior to administration of ibrutinib
2. Active uncontrolled stage 3-4 acute GI GVHD prior to administration of ibrutinib
3. Active uncontrolled stage 4 acute liver GVHD prior to administration of ibrutinib
4. Evidence of progressive disease as compared to pre-HCT (persistence of disease is permitted)
5. Anticipated planned donor lymphocyte infusion in the first 3 months post-SCT
6. Active uncontrolled bacterial or invasive fungal infections
7. Prednisone equivalent of >2mg/kg for treatment of GVHD prior to administration of ibrutinib
8. Use of second line systemic therapy for treatment of acute GVHD prior to administration of ibrutinib
9. Any life-threatening illness, medical condition, or organ system dysfunction which, in the investigator's opinion, could compromise the subject's safety, interfere with the absorption or metabolism of ibrutinib capsules, or put the study outcomes at undue risk including the presence of chronic/active HBV and HBC infections and Child-Pugh Class C.
10. Major surgery or a wound that has not fully healed within 4 weeks of starting ibrutinib

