19. REGISTRATION OF PATIENT

Each center will decide at time of study activation their preferred preparative regimens for HCT and complete the preparative regimen selection worksheet. Centers will not be allowed to deviate from their standard during the conduct of the study. Regimens will be stratified as reduced intensity (RIC), myeloablative (MAC) for related (matched and mismatched) and unrelated (matched and mismatched).

Prior to registration, a copy of the IRB approval at the site will be requested and kept on file at the

Vanderbilt-Ingram Cancer Center (VICC) Coordinating Center. Eligible participants will be entered on study centrally at the VICC Coordinating Center. All sites should email the Coordinating Center at [contact] to verify slot availability prior to enrollment.

All patients MUST be registered with the VICC prior to the start of the preparative regimen and again prior to start of protocol treatment. Registration can only be conducted during the business hours of 8AM – 5PM Central Standard Time Monday through Friday.

- 1) All sites must email the VICC CTSR Coordinating Center at [contact] to notify of upcoming registration and ensure slot availability. The following information should be included in your email:
 - Study number
 - Patient initials
 - Disease type
 - Anticipated consent date
 - Anticipated start date
- 2) If a subject ID number is required prior to patient enrollment (i.e. at screening due to sample collection requirement), the site must submit the following documents with their email notification to the Coordinating Center:
 - Copy of the patient's signed and dated Informed Consent including documentation of the consent process.
 - HIPAA authorization form (if separate from the main consent form)
 - VICC Patient Enrollment Form

The Coordinating Center will then provide a subject ID number via email.

- 3) Email the following documents to the Coordinating Center for eligibility review and patient enrollment ([contact]):
 - Copy of the patient's signed and dated Informed Consent, including documentation of the consent process.
 - HIPAA authorization form (if separate from the main consent form)
 - VICC Patient Enrollment Form
 - Eligibility supporting documents such as pathology reports, laboratory tests, etc. or EMR access. Note: all source documents should be de-identified and screening/subject ID number added prior to sending.
 - Tissue Block Registration Form (see the Lab Manual)

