 - Signed and completed Eligibility Checklist. **To be eligible for registration to the study, the participant must meet each inclusion and exclusion criterion listed in the eligibility checklist.**

Note: All study documents should be received 24-48 hours prior to the patient's anticipated start date. Same day treatment registrations will only be accepted with prior notice and discussion with the Coordinating Center. Please email the Coordinating Center if enrollment is needed sooner.

Upon satisfactory review of eligibility documents submitted, the Coordinating Center will approve enrollment and issue a subject ID number if one was not issued at screening. Once registration/enrollment confirmation from Coordinating Center is received, proceed with protocol procedures.

Please contact the assigned Study Contact with any questions regarding this process. You can also reach out to your assigned CRA once the study is activated.

The VICC Coordinating Center will assign Subject ID numbers to all patients whose eligibility has been confirmed. Only patients deemed eligible will be registered to investigational treatment.

Sequence/study ID numbers will not be re-used if a patient screen fails. Following registration, eligible participants should begin study treatment consistent with the protocol no later than [XXX days/weeks] after registration/enrollment by the VICC Coordinating Center. If a participant does not receive protocol therapy following registration within the allowed time period, the participant's registration on the study will be canceled. The Study Contact should be notified of cancellations as soon as possible. Patients being re-screened will need to consent to repeated procedures. As such, the Coordinating Center will require a new, signed Informed Consent document.

Issues that would cause treatment delays should be discussed with the Protocol Chair. Any requests for eligibility exceptions and/or deviations must be approved in writing by the Protocol Chair and the VICC DSMC.

As is generally accepted, standard of care procedures performed prior to consent, but within the protocol defined screening window for each assessment, can be used for study purposes. All research-only procedures must be performed after patient consent.

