20. STUDY SCHEDULE

Informed Consent

- The subject must read, understand, and sign the Institutional Review Board/Research Ethics Board/Independent Ethics Committee (IRB/IEC) approved informed consent form (ICF) confirming his or her willingness to participate in this study before any study-specific screening procedures are performed. Performance of procedures considered standard of care within window of screening but prior to consent will be permitted. Subjects must also grant permission to use protected health information per the Health Insurance Portability and Accountability Act (HIPAA).
- In addition, subjects must sign all approved ICF amendments per the site IRB/IEC guidelines during the course of the study.

Confirm Eligibility

- Eligibility will be confirmed pre-HCT and then second confirmation will be prior to administration of ibrutinib between day 60-90 post-HCT.
- Complete enrollment checklist and submit to coordinating center for review prior to enrollment. Preparative regimen for HCT should not be started until enrollment checklist has been reviewed and approved by coordinating center. A minimum of 48 hour notice will be mandated.

- Second confirmation: Complete enrollment checklist and submit to coordinating center for review and approval prior to start of ibrutinib between day 60-90 post-HCT. Ibrutinib will not be started until enrollment checklist has been reviewed and approved by coordinating center. A minimum of 48 hour notice will be mandated.

Pre-SCT: Screening visit:

All research studies to be completed within 4 weeks of starting preparative regimen unless specified otherwise. Timing of all pre-SCT standard of care assessments may be completed per the institutional practice.

- Standard of care: History and physical including Karnofsky performance status (KPS) (See the Clinical Assessment Manual)
- Standard of care: Transplant evaluation: follow institutional protocol on timing of evaluation prior to HCT and at a minimum will include:
 - Hematology
 - Hematology parameters performed at local laboratory will include a complete blood count: white blood cells, red blood cells, hemoglobin, hematocrit, platelets, and absolute neutrophil count.
 - Chemistry
 - Serum chemistry parameters performed at local laboratory will include: creatinine, AST, ALT, alkaline phosphatase, and total bilirubin.
 - Coagulation studies

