21. SUBJECT WITHDRAWAL

21.1 Withdrawal from Study Treatment

Study treatment will be withdrawn if:

- Patient experiences relapse or progression of underlying disease while on ibrutinib, and further continuation is not felt to be beneficial.
- Unacceptable toxicity: an intercurrent illness or adverse event that prevents further ibrutinib administration for more than 28 continuous days
- Non-compliance with taking ibrutinib or with following protocol
- Investigator decision
- Withdrawal of consent for treatment by subject
- Subject becomes pregnant
- Study termination by sponsor-investigator

All subjects, regardless of discontinuation of study treatment will undergo end of study visit and be followed for progression and survival until 2 y post HCT by imaging (CT scan and/or PET scan or other imaging) or other modalities per the discretion of the treating physician.

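### Section 24.1 does not say whether cohort A patients who never start ibrutinib are in the primary PFS analysis, and the protocol's instructions about them conflict

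*Combined protocol and SAP*

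**What the plan says.** **Analysis.** Section 24.1 restricts the primary comparison to cohort A, defined by diagnosis. It measures PFS "starting from the date of stem cell transplant (SCT" and sets the 12-month Kaplan-Meier estimate against a weighted average of historical 1-year rates (62% in CLL, 52% in MCL). No analysis set is named.

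**Entry.** Section 19 registers patients twice: "prior to the start of the preparative regimen and again prior to start of protocol treatment". Section 20 matches this: "Eligibility will be confirmed pre-HCT and then second confirmation will be prior to administration of ibrutinib between day 60-90 post-HCT". Among the criteria that bar ibrutinib at the second check, section 10 lists "Evidence of progressive disease as compared to pre-HCT (persistence of disease is permitted".

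**Text that points towards removing never-starters.** Section 19 says "If a participant does not receive protocol therapy following registration within the allowed time period", the participant's "registration on the study will be canceled". The limit is an unfilled placeholder: treatment should begin "no later than [XXX days/weeks] after registration/enrollment by the VICC Coordinating Center". Section 20 speaks of patients coming off study before ibrutinib. The heading of its 12-month visit and footnote 15 of section 22.1 treat never-starters as withdrawing, and ask of them an End of Study visit.

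**Text that points towards keeping them.** Section 21.1: "All subjects, regardless of discontinuation of study treatment will undergo end of study visit and be followed for progression and survival until 2 y" after HCT. Section 21.2 lists the reasons for leaving the study, and failing the second eligibility check is not among them.

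**The concern.** A patient must be alive and free of recognised progression to start ibrutinib. If only starters are analysed while the clock runs from transplant, each of them brings 60-90 days in which an event was largely impossible (immortal time). The historical series is described without any such selection. The comparison would then favour the trial even if the drug did nothing.

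This is the only primary comparison and there is no concurrent control, so nothing inside the trial would reveal the bias. The stated sample size of 65 enrolled does not settle the matter, because enrolment paperwork is completed at both registrations. Follow-up data lost through a cancelled registration may also be hard to recover later.

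**Working it through.** **Inputs.** Section 24.1: PFS from transplant, ibrutinib from day 60-90. Section 24.2: 65 patients, exponential PFS, two-sided level 0.05, 2 years of uniform accrual plus 2 years of follow-up, historical rate 0.55-0.59, target a 25% relative gain.

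**Step 1: reproduce the power table.** For historical 0.57 and treated 0.7125:
- Hazards are -ln 0.57 = 0.562 and -ln 0.7125 = 0.339 per year. Their cube roots are 0.8253 and 0.6973.
- With follow-up uniform on 2-4 years, Q = 65 × [1 - (e^(-2λ) - e^(-4λ))/(2λ)] = 41.0 at λ = 0.339.
- SE = 0.6973/(3√41.0) = 0.0363, taking the square root of the variance term.
- Power = Φ((0.8253 - 0.6973)/0.0363 - 1.96), about 94%; the table says 93 and simulation gives 93.3.

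The five 25% rows come out at 91.5 / 92.9 / 94.2 / 95.3 / 96.3 against 91 / 92 / 93 / 95 / 96, so the model is the plan's own.

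**Step 2: inert drug, starters only.** Let S0 be the historical rate and d the start day. The share still event-free at d is S0^(d/365). The 12-month PFS among starters, counted from transplant, is S0 / S0^(d/365). At S0 = 0.57:

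| Start day | Event-free at start | Starters of 65 | Apparent 12-month PFS | Relative gain | Share of planned 0.1425 gain |
|---|---|---|---|---|---|
| 60 | 0.912 | 59.3 | 0.625 | 10% | 39% |
| 75 | 0.891 | 57.9 | 0.640 | 12% | 49% |
| 90 | 0.871 | 56.6 | 0.655 | 15% | 59% |

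At 0.55 the apparent PFS is 0.607-0.637, and at 0.59 it is 0.643-0.672. Across the table's historical rates the relative gain is 9-16%.

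**Step 3: favourable false positives at 0.57, start day 60 / 75 / 90.**
- Exponential cube-root test, 65 enrolled, 60,000 simulated trials per case: 10 / 13 / 17%. With everyone analysed it is about 2.5%.
- Kaplan-Meier. Section 24.1 states no success rule, so assume success means a lower 95% limit above 0.57. With 65 patients this needs 45 event-free at 12 months: 45/65 = 0.692, lower limit 0.580, whereas 44/65 gives 0.563. The binomial probability of reaching 45 is 16 / 23 / 31% for 65 starters; for 65 enrolled, averaged over the number who start, it is 16 / 22 / 29%. At a true 0.57 with all 65 analysed it is 3.0%.

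**Step 4: sensitivity of the relative gain.**
- Shape of the early hazard (assumed Weibull with the same 1-year rate): gain = exp[-ln S0 × (d/365)^k] - 1. With many early events (k = 0.7) it is 16-25% across the table's rates; with few (k = 1.3) it is 5-10%.
- Missed progression. Scheduled disease reassessment falls between day 30 and day 60 (section 20), and the day 60-90 column of section 22.1 has none. Assume that half of early events are progressions seen only at that scan. A day-30 scan and day-60 start give 1/0.57^(45/365) - 1 = 7%. A day-60 scan and day-90 start give 1/0.57^(75/365) - 1 = 12%.

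**Step 5: all enrolled patients analysed and followed.** An inert drug shows 0.57, and there is no inflation.

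**The case against.** The strongest reply is that no passage plans a starters-only analysis. The clock starts at transplant, the only stated restriction is to cohort A, section 21.1 follows all subjects, and section 21.2 does not let a failed second check end participation. This stands, and it is why the size above is conditional.

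The cancellation rule in section 19 may also govern only the second registration. The surrounding text speaks of registering eligible patients to the investigational treatment and of same-day treatment registrations, which suits a step just before ibrutinib. Applied to the pre-HCT registration, any limit shorter than 60 days would cancel everyone. On this reading the rule touches only patients who pass the second check and then do not start. It does not remove those who progress or die beforehand. That reading is at least as natural as the other, but the section does not state it, and cancelling a study registration still leaves the patient's place in the analysis undefined.

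The error rates can fairly be called rule-dependent: section 24.2 uses an exponential test for power, while section 24.1 plans a Kaplan-Meier estimate without a success criterion. The time origin of the historical rates is not stated either; transplant is the natural reading.

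Two stronger inferences are tempting. One is that the trial as written will exclude early failures and is therefore biased; the documents leave this open and lean the other way. The other is that the power table is overstated because the drug starts late. If the 25% is a net gain over all enrolled patients, the table stands, and nothing in section 24.2 says otherwise.

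**Conclusion.** The point holds as an undefined analysis set with conflicting instructions on never-starters. It is not a demonstrated bias. It should be fixed before any registration is cancelled and before the primary analysis.

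If all transplanted cohort A patients are analysed, there is nothing to correct. If never-starters are dropped, the inflation shown above could supply roughly 40-60% of the targeted gain at a historical 0.57 and raise the favourable false-positive rate several-fold. Its size rests on four assumptions: a constant early hazard (5-25% relative gain under the Weibull shapes tried), recognition of progression before ibrutinib starts (less gain if it is missed), historical rates counted from transplant, and an assumed success rule for the Kaplan-Meier error rates.

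**What to change.** - **Section 24.1:** define the primary set as all cohort A patients registered before HCT and transplanted. Keep PFS from transplant, and count progression or death before ibrutinib as an event.
- **Section 19:** say which registration the cancellation rule governs, and fill in or remove the placeholder.
- **Sections 19, 20 and 22.1 (footnote 15), against 21.1 and 21.2:** state that neither cancellation nor the End of Study visit removes or censors a never-starter, who is followed for progression and survival to at least 12 months.
- **Any starters-only analysis:** report it as supporting, from a landmark at ibrutinib start, against a historical rate conditional on being event-free at the same landmark (about 0.625-0.655 at 0.57 under the exponential model). Note that this does not match the other criteria of the second check.
- **Section 24.2:** say whether the 25% is net over all enrolled patients. If so, the power table needs no change.

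The cost is wording, plus status follow-up of never-starters that section 21.1 already implies. Including them dilutes any effect of the drug somewhat; that is the price of a like-for-like comparison with history.

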24.2 Sample Size

The following table reflects the power and effect size, if we enroll 65 patients with varying proportion of the diagnoses. **These calculations are based on the maximum likelihood estimator (MLE) for the mean survival time assuming exponentially-distributed PFS⁵³ using the cube-root transformation of the MLE as suggested by Spratt⁵⁴. The one-year survival probability can be calculated once the distribution is specified.** The following test statistic has a standard normal distribution:

$$\frac{\hat{\phi} - \phi}{(\hat{\phi}^2/9\hat{Q})^{1/3}} \sim N(0,1),$$

where $\hat{\phi} = \hat{\theta}^{-1/3}$, $\hat{\theta}$ is the MLE for the PFS mean, and $\hat{Q} = \sum(1 - e^{-L_i/\hat{\theta}})$.

This is a single arm phase two study. Patients will be accrued uniformly over two years, and then followed for two years. The power calculations are based on derivations from Lawless⁵³ with a cube-root transformation of the maximum likelihood estimate (MLE), as suggested by Spratt⁵⁴. This is implemented in the online calculator (tool of One Arm Survival) found at <https://stattools.crab.org> which is provided by the SWOG Statistical Center. Thus, 65 patients will give us at least 84% power to detect an effect size of 25% improvement in progression-free survival at 1 year compared to the estimated historical control rate, for varying proportions of patients with CLL and MCL. The following table reflects the power and effect size, if we enroll 65 patients with varying proportion of the diagnoses.

Table: Power achieved for a sample of 65 patients for different effect sizes using a 2-sided parametric test with level 0.05, assuming on 2 years of uniform accrual and 2 years of follow-up time.

	%CLL	%MCL	1 year PFS Historical Control	1 year PFS Treated	Power
20%	30	70	0.55	0.660	74
	40	60	0.56	0.672	76
	50	50	0.57	0.684	78
	60	40	0.58	0.696	80
	70	30	0.59	0.708	83
25%	30	70	0.55	0.688	91
	40	60	0.56	0.700	92
	50	50	0.57	0.713	93
	60	40	0.58	0.725	95
	70	30	0.59	0.738	96
30%	30	70	0.55	0.715	98
	40	60	0.56	0.728	98
	50	50	0.57	0.741	99
	60	40	0.58	0.754	99
	70	30	0.59	0.767	99

In addition, cohort B will include 10 patients (FL and HD). There is no formal sample calculation for cohort B.

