6.5 Dose and Administration

Ibrutinib will be administered at a dose of 420 mg by mouth once a day starting between day 60-90 post HCT and continue until 1y post HCT. Ibrutinib is dispensed as 140 mg capsules and patients will be

instructed to take 3 capsules by mouth once a day. Patients will be instructed to take the drug at approximately the same time every day. Patients will be instructed to swallow the capsules whole with water and not to open, break or chew the capsules.

If a dose of ibrutinib is not taken at the scheduled time, it can be taken as soon as possible on the same day with a return to the normal schedule the following day. Extra capsules of ibrutinib should not be taken to make up for the missed dose.

For patients on azoles, the starting dose will be 140 mg by mouth once a day starting between day 60-90 post HCT and continue until 1y post HCT.

Patients using Posaconazole as outlined in section 11.2 will start ibrutinib at a dose of 70 mg by mouth once a day between day 60-90 post HCT and continue until 1 year post HCT.

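### Section 24.2 takes its 91–96% power from an exponential test over 2–4 years, although the endpoint and the drug both end at month 12; the planned 12-month comparison has about 63–77%

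*Combined protocol and SAP*

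**What the plan says.** Section 24.2 claims that "65 patients will give us at least 84% power to detect an effect size of 25% improvement in progression-free survival at 1 year" and prints a table with higher values for the same effect: 91, 92, 93, 95 and 96% for historical rates 0.55 to 0.59. The table is described as "using a 2-sided parametric test with level 0.05", and the calculation is based on the maximum likelihood estimate "for the mean survival time assuming exponentially-distributed PFS". Its follow-up assumption is: "Patients will be accrued uniformly over two years, and then followed for two years".

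Three other sections bear on this:

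- Section 6.5 gives ibrutinib "once a day starting between day 60-90 post HCT and continue until 1y post HCT".
- Section 24.1 counts PFS from the transplant date. It plans a Kaplan-Meier estimate of the 12-month rate with a Greenwood 95% confidence interval, to be compared with the weighted historical rate.
- Section 21.1 has all subjects "be followed for progression and survival until 2 y post HCT".

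**The concern.** A single exponential for treated patients means that one reduced hazard acts from day 0 to the end of follow-up. The dosing schedule leaves the first 60 to 90 days and all time after month 12 without drug. The primary endpoint also ignores everything after month 12. Much of the information behind the printed power therefore comes from a period that neither the treatment nor the endpoint covers.

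The printed power is the stated justification for 65 patients. If the planned analysis has much less, a negative result would be read as stronger evidence against ibrutinib than it is.

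**Working it through.** **Inputs.** N = 65, two-sided 0.05, historical 1-year PFS S0 = 0.55 to 0.59, treated S1 = 1.25 × S0, 2 years of uniform accrual plus 2 years (section 24.2); drug window from day 60–90 to month 12 (section 6.5); PFS from transplant (section 24.1).

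**1. Reproducing the table.** Let λ0 = −ln S0, λ1 = −ln S1 and φ = λ^(1/3). The expected events are Q = 65 × [1 − (e^(−2λ1) − e^(−4λ1))/(2λ1)], and SE = φ1/(3√Q). The denominator of the printed statistic reads with exponent 1/3; a square root is used here because it reproduces the table.

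For S0 = 0.55: λ0 = 0.598, λ1 = 0.375 and Q = 43.4. Then φ0 = 0.842, φ1 = 0.721 and SE = 0.0365. Power = Φ(0.1215/0.0365 − 1.96) = 91.5%.

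Across the five 25% rows the formula gives 91.5, 92.9, 94.2, 95.3 and 96.3%, and simulation gives 90 to 96%. The printed values are 91, 92, 93, 95 and 96%. The table's arithmetic is sound for its model.

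**2. Where the events fall.** Events by month 12 are 65 × (1 − S1).

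| S0 | S1 | Total events | By month 12 | After month 12 |
|---|---|---|---|---|
| 0.55 | 0.6875 | 43.4 | 20.3 | 23.1 (53%) |
| 0.57 | 0.7125 | 41.0 | 18.7 | 22.3 (54%) |
| 0.59 | 0.7375 | 38.5 | 17.1 | 21.5 (56%) |

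Events before day 60–90 add another 8–13%, so the drug window holds 32–38%.

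**3. The exponential test with the 25% target met.** Simulated trials of 65 patients, followed for 2–4 years. The hazard is historical to day 75, then reduced so that PFS at month 12 equals 1.25 × S0. The documents give no PFS beyond 1 year, so the hazard after month 12 is an assumption:

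| Hazard after month 12 | Power, S0 = 0.55 / 0.57 / 0.59 |
|---|---|
| On-drug hazard persists | 96 / 98 / 99% |
| 0.5 × historical first-year rate | 97 / 98 / 98% |
| 0.75 × historical first-year rate | 73 / 74 / 77% |
| Historical first-year rate | 29 / 32 / 33% |

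A falling hazard that is unrelated to the drug would count in the drug's favour too. With no drug effect and a post-month-12 hazard of 0.75 × the first-year rate, this test favours ibrutinib in about 17% of trials, against a nominal 2.5%.

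**4. The planned 12-month comparison.** Section 24.1 gives no explicit decision rule, so success is taken as a lower 95% limit above S0. With no censoring before month 12, the Kaplan-Meier estimate is x/65 and Greenwood's variance is binomial. Success requires x/65 − 1.96 × √[(x/65)(1 − x/65)/65] > S0. For S0 = 0.55, x = 44 gives a lower limit of 0.563 and is the smallest count that succeeds.

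| S0 | S1 | Smallest x | Power, P(X ≥ x) | Printed |
|---|---|---|---|---|
| 0.55 | 0.6875 | 44 | 63% | 91% |
| 0.56 | 0.7000 | 44 | 71% | 92% |
| 0.57 | 0.7125 | 45 | 70% | 93% |
| 0.58 | 0.7250 | 45 | 77% | 95% |
| 0.59 | 0.7375 | 46 | 76% | 96% |

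These values depend only on PFS at month 12, not on the shape of the hazard. Log-log limits would give 53, 60 and 66% at 0.55, 0.57 and 0.59.

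**5. The on-drug effect implied.** The table's constant hazard ratio is λ1/λ0 = 0.627 to 0.577. If the hazard before the first dose is historical and a = (start day)/365, the same 12-month PFS needs an on-drug ratio of (λ1/λ0 − a)/(1 − a). At S0 = 0.55 this is 0.55 for day 60 and 0.505 for day 90. At S0 = 0.59 it is 0.49 and 0.44.

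**6. Two-year follow-up.** With every patient followed for exactly 2 years, Q = 65 × (1 − e^(−2λ1)), and the constant-hazard power is 84, 86, 88, 89 and 91%. The minimum equals the 84% in the text of section 24.2, which the table's 91–96% does not.

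**The case against.** The plan defines its effect as net PFS at 12 months from transplant, so events before the first dose are already inside the target. This stands: if the target is met, pre-dose time takes no power from the 12-month comparison.

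A reader might apply the table's hazard ratio only from the first dose and conclude that power collapses. That substitutes a gain of about 19% for the stated 25%; no section gives an on-drug hazard ratio of 0.58–0.63 as the assumed effect.

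A reader might also infer that the printed power cannot be reached at all. The documents do not support that for the exponential test. Section 5.3 expects the graft-versus-tumour effect to be established by month 12, and a persisting on-drug hazard gives 96–99%. Values near 30% require a return to the full first-year historical hazard, which is possible but nowhere stated.

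The analysis set is open as well. Patients are registered before conditioning and again before ibrutinib (section 19), and no section says whether non-starters count in the primary analysis. If only starters were analysed there would be no pre-dose events, and the 0.44–0.55 requirement would not apply. The comparison with historical rates counted from transplant would then favour the trial.

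Finally, the 42.9% discontinuation in section 6.3.3 should not be carried over: it comes from patients with established steroid-dependent or refractory chronic GVHD.

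**Conclusion.** The point holds in this form. The printed 91–96% is correct arithmetic for a constant-hazard exponential test over 2–4 years, but it is not the power of the analysis that section 24.1 plans. That analysis has about 63–77% at the full 25% target, 18 to 28 points below the table. This assumes plain Greenwood limits, no censoring before month 12, a fixed historical rate and the success rule in step 4.

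For the exponential test, the printed power accompanies a 25% net gain only if the hazard after month 12 is also well below the first-year historical rate, an assumption the plan does not state. The required on-drug hazard ratio of 0.44–0.55 rests on a constant historical hazard, no effect before the first dose, and analysis of all transplanted patients.

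**What to change.** In section 24.2:

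- Replace the printed power and the 84% sentence with the power of the planned 12-month Kaplan-Meier comparison for 65 patients. Name the type of confidence limit and the success rule.
- If the exponential calculation is kept as supportive, use a piecewise hazard with a stated assumption after month 12. Use the 2-year follow-up of section 21.1, for which the constant-hazard reference is 84–91%.
- State the on-drug hazard ratio that a 25% net gain requires, and the analysis set it assumes.

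The cost is one recalculation and a short rewording. The downside is a less favourable stated power. Sample size, dosing and endpoint stay as they are.
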